4.3 Criteria for women of childbearing potential

4.3.1 Acceptable methods of contraception

To ensure compliance, the study personnel must remind women of childbearing potential at each visit to use the methods of contraception defined for this study.

Females of child-bearing potential require the use of highly effective contraceptive measures (failure rate of less than 1% per year), from screening up to 6 months after the last study drug administration:

Highly effective contraceptive measures include:

- Sexual abstinence: refraining from heterosexual intercourse during the entire period defined above. The reliability of sexual abstinence needs to be evaluated in relation to its duration and compatibility with the preferred and usual lifestyle of the subject. Periodic abstinence (calendar, symptothermal, post-ovulation methods) is not an acceptable method of contraception.
- Hormonal contraceptives: combination or progesterone only.
- Intrauterine methods: intrauterine devices or systems.
- Bilateral tubal occlusion.
- Vasectomized partner.

The methods of birth control used (including non-pharmacological methods) must be recorded in the electronic Case Report Form (eCRF).

5 INVESTIGATIONAL MEDICINAL PRODUCT

5.1 Description of Investigational Medicinal Product

Emapalumab (previously referred to as NI-0501) is a fully human anti-IFN γ monoclonal antibody that binds to and neutralizes human IFN γ .

Emapalumab is manufactured by a third-party manufacturing facility duly qualified by Sobi AG and is supplied as described in the IMP Manual. Vials are filled single-use glass vials which require a dilution prior to administration.

The nominal composition of the emapalumab sterile concentrate for infusion (per mL) is as follows:

Ingredient	Quantity (per mL)
Emapalumab	5 mg or 25 mg
L-Histidine	1.55 mg
L-Histidine monohydrochloride, monohydrate	3.14 mg
Sodium chloride (NaCl)	7.31 mg
Polysorbate 80	0.05 mg
pH	6.0 \pm 0.2

The solution contains no antimicrobial preservative, and therefore each vial must be used only once.

5.2 Investigational Medicinal Product Handling

5.2.1 Packaging and Labeling

Emapalumab will be supplied to study sites in glass vials containing 10 mL or 20 mL solution at a concentration of 5 mg/mL or 25 mg/mL. Labeling and packaging will be prepared to meet local regulatory requirements. The Investigational Medicinal Product (IMP) Manual provides further details.

5.2.2 Investigational Medicinal Product Supply

Emapalumab will be supplied to the study sites as open-label supplies.

5.2.3 Receipt, storage, preparation and administration

Emapalumab receipt, storage, preparation, administration will be described in details in the IMP manual.

5.2.3.1 Receipt and storage

The emapalumab vials will be transported with temperature monitoring device, in order to ensure consistent temperatures during transit. When the study drug is received at the site, the Investigator or Pharmacist will check for accurate delivery and absence of temperature deviation alarms.

The study drug should be stored between 2 – 8 °C (36 – 46 °F). All vials must be stored in a secure locked location in a temperature-controlled refrigerator or cold room. Any deviations from the recommended storage conditions should be immediately reported to the Sponsor and responsible study clinical research associate (CRA). Affected vials should not be used and should be quarantined until the Sponsor has authorized their use, return or destruction.

Documentation of the storage conditions of the study drug must be maintained over the timeframe the study drug is stored at the site, until such time as it is used, disposed of, or returned to Sobi AG or designee.

Regular inspections of the emapalumab vials are required, as detailed in the IMP manual. For guidance on the Preparation and Administration of Individual Doses of Study Drug emapalumab refer to the IMP manual.

5.2.3.2 Preparation

The study drug must be prepared only by a Pharmacist or other appropriately qualified staff member, specifically authorized by the Investigator/Pharmacist and appropriately licensed to perform the task.

The specific dose to be administered for an individual infusion is determined as detailed in section 5.4. As emapalumab is dosed in mg/kg, the weight of the patient must be taken within 24 hours of the preparation of the study drug for administration.

Full instructions for the preparation, including dilution steps, and method for administration of emapalumab are available in the IMP Manual that will be provided to all investigational sites.

5.2.3.3 Administration

The patient should receive the designated volume of the infusion material through an infusion pump over 1 to 2 hours depending on the volume to infuse. A 0.2 µm filter must be included in all infusion lines.

It is recommended that an IV central line remains in place to ensure venous access during the treatment period. This will improve patient's comfort and ensure a reliable drug administration. However, peripheral infusions have been successfully performed in some patients.

Since no data are available on the compatibility of emapalumab with other IV substances or additives, other medications/substances should not be added to the infusion material or infused simultaneously through the same IV line. If the same IV line is used for subsequent infusions of other drugs, the line should be flushed appropriately with saline before and after infusion of emapalumab.

The infusion of emapalumab will be performed under the direct supervision of the Investigator (or delegate), preferably in the morning and preferably at the same time for each infusion, in an environment with access to emergency equipment and trained medical personnel.

Details of the infusion must be recorded in the patient's Medical Notes or other source documents and have to include:

- Dose prescribed (in mg/kg).
- Date of administration.
- If flushing was performed.
- Start time & End time.
- Rate of administration.
- Total volume infused (ml).
- Total dose infused (mg).
- In case infusion was interrupted:
 - reason for interruption.
 - the stop time of the infusion.
 - the new start time of the infusion.
 - the new rate of administration.
- Any untoward signs and/or symptoms, event or illness experienced by the patient during the infusion.
- Any other event(s) judged relevant by the site personnel.

In the event that a patient experiences an infusion-related reaction (IRR), the infusion may be halted (as per Investigator's judgment) and symptomatic treatment may be administered.

The decision to restart the infusion will be based on the evolution of the patient's status and on the physician's own medical judgment. The infusion will be restarted at half of the rate being used at the time of onset of the IRR.

All changes in infusion rate will be recorded in the patient's medical chart and the eCRF: each time at which there is a rate modification, as well as end time of the premature or delayed termination of the infusion.

Unless related to a hypersensitivity reaction, a local infusion issue (such as catheter displacement, obstruction or product extravasation) will trigger the infusion of the remaining quantity through a new venous access as soon as possible. All information related to the incident will be recorded accurately in the patient's medical chart prior to being entered in the eCRF. This includes reasons, volume of IMP potentially lost, time of infusion stop, time at which the infusion was resumed and time of end of the infusion.

5.2.4 IMP Accountability and Destruction

5.2.4.1 Accountability

When the study drug is received at the site, the Investigator or Pharmacist (or appropriate designee) should acknowledge its receipt by signing (or initialing) and dating the documentation. Documentation should be returned to Sponsor (or designee) and a copy retained in the Investigator's file.

The dispensing of the study drug shall be carefully recorded on Drug Accountability Forms and an accurate accounting must be available for verification by the CRA at each monitoring visit.

Drug accountability records shall include:

- Confirmation of the study drug's delivery to the study site.
- The inventory at the study site.
- The use of study drug by each patient.
- Proper storage conditions at the study site.
- The return to the Sponsor or alternative disposition of unused products.

The records should include dates, quantities, expiration dates, batch number, and patient number.

Unused study drug must not be discarded or used for any purpose not authorized by the Sponsor.

5.2.4.2 Destruction, Return and Disposal

Periodically during the study and at the conclusion of participation of the study by the site, the CRA will monitor and collect the Drug Accountability Forms, before making arrangements for study drug return or authorization of destruction by the study site.

5.3 Rationale for Dosing Regimen

The PK and PD of emapalumab have been studied in primary HLH patients. It has been shown that emapalumab significantly decreased the concentrations of CXCL9. The PK and PD of emapalumab are influenced by IFN γ production. The higher the IFN γ production, the higher the clearance and the concentration of emapalumab required to reach the same level of CXCL9. In primary HLH patients, total IFN γ concentrations varied markedly (from 10² to 10⁶ pg/mL) between subjects and within subjects as a function of time, indicating a sustained and variable IFN γ production. This required administration of emapalumab twice-a-week until HSCT and adaptation of the dose between 1 and 10 mg/kg.

In addition to the IFN γ production, population PK analyses of data obtained in HLH patients identified body weight (highly correlated to age) as the main factor influencing emapalumab PK. As emapalumab doses are administered in mg/kg, no additional dose adaptation is required in adults as compared to young children.

In an ongoing study (NI-0501-06) in sJIA in patients developing MAS, emapalumab is administered intravenously at an initial dose of 6 mg/kg and continued at 3 mg/kg for up to 4 weeks. Initial results suggest that in sJIA patients developing MAS, emapalumab administration not only neutralizes IFN γ activity, as indicated by normalization of CXCL9, and leads to a decrease in IFN γ production.

Given the pathophysiology of GF, it is likely that IFN γ production is acute and not sustained. However, the exact levels of IFN γ production in patients with various underlying diseases experiencing GF may vary within and between patients and it is unknown at this time if pre-emptive treatment with emapalumab may affect IFN γ

production and profile over time in this context. In addition, various degrees of chimerism can be expected prior to GF and varied IFN γ production may be observed. Because of the known impact of IFN γ production on emapalumab PK and PD, the Sponsor intends to characterize the level and evolution of IFN γ production in this study to define the appropriate emapalumab dosing regimen for prevention of allogeneic HSCT GF.

To determine the emapalumab dosing regimen for the first cohort, the following elements have been taken into consideration:

- The initial dose of emapalumab should be high enough to limit loss of donor cells and to allow rapid reversal of the GF process which is likely to have already started upon elevation of CXCL9 in the patients at risk
- IFN γ activity should be neutralized during the entire engraftment period (ranging from 2 to 6 weeks, depending on the stem cell source)
- Prolonged administration should be limited to allow full graft-versus-tumor activity (for patients transplanted for hematological malignancies) and anti-infectious activity of the graft after successful HSCT.

To achieve rapid IFN γ neutralization, an initial dose of 6 mg/kg emapalumab will be administered. To maintain further IFN γ neutralization covering the duration of engraftment, emapalumab administration will be continued at a dose of 3 mg/kg after 3 days (second infusion) and every 3 or 4 days thereafter until stable engraftment has been achieved or until a maximum of 15 doses. This definition of treatment duration will guarantee that patients are treated until the graft has clearly engrafted but not beyond.

A similar dosing regimen consisting of a loading dose of 6 mg/kg and maintenance doses of 3 mg/kg for up to 4 weeks is currently being investigated in MAS/sJIA patients (study NI-0501-06).

To further support the proposed dosing regimen, simulations were performed based on the currently available PK and PK/PD models assuming either a sustained or a decreasing IFN γ production, as observed in primary HLH patients or MAS/sJIA patients, respectively.

Simulations were performed with a dosing duration of 2 weeks (Figure 3) and of 6 weeks (Figure 4). The upper graphs in the figures show the simulations in the case of a sustained IFN γ production. The graphs at the bottom show the simulations performed assuming a decrease in IFN γ production over time.

- On the left-hand side graphs, the total IFN γ concentrations are given as a function of time for initial total IFN γ concentrations of 10,000 pg/mL (orange lines), 50,000 pg/mL (blue lines) and 250,000 pg/mL (green lines).
- On the graphs in the middle, the emapalumab concentrations are given as a function of time for a body weight of 5 kg (dashed lines) and 70 kg (solid lines) and initial total IFN γ concentrations of 10,000 pg/mL (orange lines), 50,000 pg/mL (blue lines) and 250,000 pg/mL (green lines). The grey area indicates the mean of the individual three highest peak and trough concentrations observed in Studies NI-0501-04 and NI-0501-05 and in CU patients (cut-off date 20 July 2017).
- On the right-hand side graphs, the CXCL9 concentrations are given as a function of time for a body weight of 5 kg (dashed lines) and 70 kg (solid lines) and initial total IFN γ concentrations of 10,000 pg/mL (orange lines), 50,000 pg/mL (blue lines) and 250,000 pg/mL (green lines). The black dashed line indicates a CXCL9 level of 300 pg/mL.

Figure 3: PK and PD simulations assuming a sustained IFN γ production (upper panel) or decreasing IFN γ production (lower panel) for an emapalumab dosing duration of 2 weeks

[figure not shown]
[figure not shown]

Figure 4: PK and PD simulations assuming a sustained IFN γ production (upper panel) or decreasing IFN γ production (lower panel) for an emapalumab dosing duration of 6 weeks

The results of the simulations indicate the following:

- In patients with a sustained IFN γ production, emapalumab treatment initiation leads to a rapid decrease in CXCL9. Subsequently CXCL9 remains at a stable level, which is determined by the magnitude of the underlying IFN γ production. Upon dosing discontinuation, emapalumab levels decrease and CXCL9 levels start increasing again. Emapalumab clearance and the concomitant increase in CXCL9 are more pronounced in patients with a high IFN γ production.
- In patients with a decreasing IFN γ production, the contribution of the target-mediated clearance to the overall clearance of emapalumab is limited. Emapalumab treatment initiation leads to a rapid decrease in CXCL9. However, in these patients the decrease in CXCL9 is more pronounced as compared to patients with a sustained IFN γ production, because it is driven by the emapalumab-induced neutralization of free IFN γ as well as the decrease in IFN γ production. Upon treatment discontinuation, emapalumab clearance is slow, reaching normal linear clearance, while CXCL9 levels remain low.

The simulations performed demonstrate the importance of the evolution of the IFN γ production on the selection of the appropriate dosing regimen in emapalumab-treated patients. Based on these simulations, emapalumab treatment for up to 6 weeks will be needed in order to neutralize IFN γ during the entire engraftment period in patients with sustained IFN γ production. An initial emapalumab dose of 6 mg/kg followed by 3 mg/kg is predicted to neutralize IFN γ in patients with total IFN γ levels of 10,000 pg/mL, which is considered a reasonable rationale for selecting this dose regimen for Cohort 1.

Since higher dose levels of emapalumab will be required to neutralize IFN γ in patients who would present higher IFN γ levels (e.g. up to 250,000 pg/mL), the proposed dose regimens to be used in Cohort 2 and 3 are higher than in Cohort 1. The dose levels could be increased in 2 different ways. The initial dose 6 mg/kg may be given for a longer period (either for 3, 6, 9 or 15 doses) before decreasing to a lower maintenance dose of 3 mg/kg. Or, as an alternative, both the initial dose level and the maintenance dose level may be increased to 10 mg/kg for 3 doses followed by a maintenance dose of 6 mg/kg (Table 4).

The highest potential dose level is 10 mg/kg for 3 doses followed by 6 mg/kg up to no more than 15 doses. As described in the current version of the IB, a dose up to 10 mg/kg daily have been administered with no reported safety concern so far.

5.4 Dosing Regimen

Patients entering the monitoring or extended monitoring period and fulfilling the criteria to be pre-emptively treated for primary or secondary graft failure (as outlined in section 3.4.3) will receive emapalumab as described below:

- Emapalumab will be administered by IV infusion over 1 to 2 hours depending on the volume of the infusion.
- The first infusion must be performed within 12 hours from CXCL9 sample collection time (with levels above defined threshold).
- Treatment will last until maximum dose 15 (up to 56 days) or until evidence of engraftment, whichever comes first.
- The first cohort of patients will receive a first infusion of 6 mg/kg at treatment day 0 (TD0), followed by a second infusion at 3 mg/kg after 3 days (TD3). Subsequent infusions of 3 mg/kg will be every 3 or 4 days (from previous dose) until dose 15 or until engraftment.
- A maximum of 2 additional cohorts may be added to allow dosing regimen adaptation based on the PK/PD observed from the previous cohort(s). Efficacy and safety data will also be considered before adding additional cohorts.
- The dose regimen options for cohort 2 or cohort 3 are presented in Table 4.
- Patients optionally treated for secondary graft failure will receive the same dose as the patients treated for primary graft failure.

Table 4: dose regimen options in cohort 2 or 3

Cohort 2 or Cohort 3	Option 1 6 mg/kg for 3 doses followed by 3 mg/kg from dose 4 until dose 15 or until engraftment
	Option 2 6 mg/kg for 6 doses followed by 3 mg/kg from dose 7 until dose 15 or until engraftment
	Option 3 6 mg/kg for 9 doses followed by 3 mg/kg from dose 10 until dose 15 or until engraftment
	Option 4 6 mg/kg for 15 doses or until engraftment
	Option 5 10 mg/kg for 3 doses followed by 6 mg/kg from dose 4 until dose 15 or until engraftment

6 BACKGROUND THERAPY AND CARE

6.1 Infection prophylaxis

- Patients must receive prophylactic treatment for Herpes Zoster prior to initiation of emapalumab treatment. Prophylaxis should be maintained until approximately 2 emapalumab half lives (i.e. approximately 44 days) after end of treatment
- In case a patient, previously vaccinated for tuberculosis, shows a Purified Protein Derivative (PPD) test result ≥ 5 mm and a negative IFN γ -release assay, patients will receive TB prophylaxis according to local medical practice.

6.2 Authorized treatments

The following treatments are allowed during the study:

- Prophylaxis and therapy of infections (antibiotics, antifungal and anti-viral) as per local medical practice.
- Conditioning (myeloablative conditioning [MAC], RIC or NMA) prior to HSCT as per local medical practice.
- GvHD prophylaxis and treatment as per local medical practice..
- Steroids during monitoring, extended monitoring and follow up.
- During emapalumab treatment only topical steroids are allowed and methylprednisolone up to 2 mg/kg/day (or other equivalent steroid dose) for not more than 2 days.
- Hematopoietic growth factors, stem cell boost, donor lymphocyte infusion (DLI).
- Intravenous immunoglobulin (IVIG) is only allowed as replacement treatment (i.e. not at doses expected to produce an immunomodulatory effect) based on medical judgment.
- Analgesic treatment, transfusion of blood products, electrolyte and glucose infusions, IV parenteral nutrition, inotropic support, ultrafiltration or hemodialysis.

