Patients with CXCL9 levels below threshold will be monitored and will enter follow up for non-emapalumab treated patients at the end of the monitoring periods. This additional group of patients will allow to confirm the frequency of GF when CXCL9 levels are below threshold.

In clinical practice, GF is usually not confirmed until at least day 21 and up to 42 days following HSCT, therefore the monitoring period for primary GF will last up to 42 days. As soon as an ANC is ≥ 500 cells/ μL , patients will enter the extended monitoring period for secondary GF which will last up to 98 days. ANC increase can occur within 10 days after HSCT, but may take up to 30-40 days, mostly depending on the source of stem cells. Secondary GF, which may occur after initial engraftment, is usually observed within the first few months after transplant, therefore the extended monitoring will last up to 98 days.

To achieve rapid IFN γ neutralization, an initial dose of 6 mg/kg emapalumab will be administered. To maintain further IFN γ neutralization covering the duration of engraftment, emapalumab administration will be continued at a dose of 3 mg/kg after 3 days (second infusion) and every 3 or 4 days thereafter until stable engraftment has been achieved or until a maximum of 15 doses. This definition of treatment duration will guarantee that patients are treated until the graft has clearly engrafted but not beyond. Further details on the dose regimen rationale can be found in section 5.3.

Patients treated pre-emptively for secondary graft failure will receive the same dose regimen as patients treated pre-emptively for primary graft failure in the 3 cohorts.

Patients will be followed up until 3 years post HSCT in order to collect survival data, occurrence of GvHD and use of defined treatments or procedures to support the graft function post-transplant.

Patients will be stratified at screening into two groups in order to include at least 40% malignant and 40% non-malignant. Stratification will allow to explore the appropriate dose inhibiting IFN γ production in a similar number of patients presenting malignant or non-malignant disease in each cohort. Patients below 1 year are considered more vulnerable and will therefore not be included in the study until the safety has been confirmed in patients 1 year or older.

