3.4.4 Treatment Period

Assessments to be performed during the treatment period are detailed in the Schedule of Assessments (Table 6a and Table 6b).

Criteria to enter treatment during the monitoring and extended monitoring period, and not to start treatment, are defined in section 3.4.3.

- Patients treated for primary or secondary GF will receive emapalumab for maximum 15 infusions or until engraftment is confirmed.
- Engraftment is defined as ANC \geq 500 cells/ μ L for 3 consecutive measures and donor chimerism above 60% (for primary GF) or ANC \geq 500 cells/ μ L for 3 consecutive measures and 2 consecutive measures of donor chimerism above 60% or 7 days of platelets above 20000 cells/ μ L without transfusion (for secondary GF).
- Preferably, ANC recovery should be based upon three consecutive laboratory values (ANC sample drawn 1 or 2 days apart maximum).
- Patients must be hospitalized in case of active infections requiring IV antimicrobial therapy during treatment.
- If engraftment is confirmed prior to the last dosing day (dose 15) or if patients discontinue treatment, patients will perform all assessments as per end of treatment visit (EoT) and can be discharged if hospitalized provided that there is no active infections requiring IV antimicrobial therapy.
- Patients who take prohibited medications will not be discontinued from emapalumab treatment unless for medical reasons.
- Pre-emptive treatment for secondary GF is optional and it is investigator's responsibility to decide whether to start pre-emptive treatment with emapalumab or not.

End of Treatment (EoT) visit

Assessments to be performed during the EoT visit are detailed in the Schedule of Assessments (Table 6a and Table 6b).

Patients who discontinue treatment or engraft before the last dosing day (dose 15) will attend the EoT visit. Patients who complete treatment until dose 15 will not be required to undergo an EoT visit.

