6.3 Prohibited treatments

The following treatments are not allowed **during emapalumab treatment**:

- Methylprednisolone more than 2 mg/kg/day (or other equivalent steroid dose) for more than 2 days.

The following treatments are not allowed during **monitoring/extended monitoring and during emapalumab treatment**:

- All kinase inhibitors.
- Interferon gamma-1b.
- Biologic drugs (except rituximab used to treat EBV infection or to remove B-cells producing donor specific antibodies).

The following treatments are not allowed **during the study up to 6 months after the last emapalumab dose or until the end the monitoring period for untreated patients**:

- Live or attenuated (including BCG) vaccine.

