7 STUDY END POINTS

The main objective is dual and is composed of:

- Dose selection.
- Preliminary efficacy of emapalumab treatment pre-empting GF.

The endpoints used to assess dose selection are:

- Serum concentrations of free emapalumab.
- Serum concentration of total IFN γ .
- Serum concentration of CXCL9.

The main endpoint used to preliminarily assess efficacy of emapalumab in pre-empting GF is:

- Occurrence of primary GFs from start of treatment up to end of treatment.

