11.1.4 Non-evaluable patients

The following cases represent non-evaluable patients when treated for primary GF:

- Administration of any prohibited medication during treatment.
- Premature treatment withdrawal for reasons other than safety or lack of efficacy.
- More than 1 infusion missed.

- Documented delay of treatment initiation by more than 36 hours after CXCL9 sample collection time and levels above threshold.

Recruitment of patients treated for primary GF will continue until the required number of evaluable patients for each interim analysis and final analysis is met.

This definition of non-evaluable patients does not apply for patients treated for secondary GF.

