12.2 Interim analyses

Interim analyses (IAs) are planned when the last patient completes pre-emptive treatment for primary GF in a cohort (4 evaluable patients). Total IFN γ levels, CXCL9 levels and PK/PD data will be assessed for inclusion of additional dose cohorts. The benefit risk of emapalumab will be assessed by IDMC and sponsor before transitioning to the next dose regimen in cohort 2 or 3.

Once the appropriate dose regimen is determined in cohort 1, 2 or 3, a maximum of 6 additional evaluable patients may be added to the selected cohort. Additional IAs are planned when 7 and 10 evaluable patients have completed treatment with the selected dose, unless the study is stopped for futility or success. A final analysis with all data collected up to EoS will be included in a CSR.

IAs will be also performed after 1 and 2 years follow up calls and data collected up to 3 years follow up will be included in an addendum to the CSR.

Given that similar PK/PD profile of emapalumab is expected in patients treated to pre-empt primary and secondary GF, data obtained in the secondary GF patients may also be used.

The following guidance will be followed for inclusion of additional patients to the same cohort (once the appropriate dose has been selected) or to stop the study for futility or success.

After 4 evaluable patients have completed treatment for primary GF in a cohort with selected dose:

- 3 or more patients experienced GF, the study will be stopped for futility.
- 0 to 2 patients experienced GF, 3 additional patients may be added.

After 7 evaluable patients have completed treatment for primary GF:

- 5 or more patients experienced GF, the study will be stopped for futility.
 - 2 to 4 patients experienced GF, 3 additional patients may be added.
- 0 to 1 of the patients experienced GF, the study can be stopped for success.

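### A graft that takes after a stem cell boost or DLI given during emapalumab treatment is not a graft-failure event on the supplied text, and no stated rule separates such patients at the 4- and 7-patient looks

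*Combined protocol and SAP*

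**What the plan says.** Section 6.2 opens with "The following treatments are allowed during the study" and includes the line "Hematopoietic growth factors, stem cell boost, donor lymphocyte infusion (DLI". In the same list, steroids are limited by period and dose, and IVIG by purpose; this line carries no limit. For monitoring and emapalumab treatment, section 6.3 bars kinase inhibitors, interferon gamma-1b and "Biologic drugs (except rituximab used to treat EBV infection or to remove B-cells producing donor specific antibodies"; it also sets a steroid limit and a live-vaccine ban. It does not name boost or DLI.

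The only medication criterion for non-evaluability in section 11.1.4 is "Administration of any prohibited medication during treatment". Section 12.4 repeats it and makes the evaluable patients the primary analysis population. Section 3.4.4 defines engraftment as ANC of at least 500 cells/μL "for 3 consecutive measures and donor chimerism above 60% (for primary GF", with no condition on how that state was reached.

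The main efficacy endpoint in section 7 is "Occurrence of primary GFs from start of treatment up to end of treatment". Section 12.2 counts patients who experienced GF. At 4 patients, 3 or more means futility. At 7, 5 or more means futility, 2 to 4 means that three more may be added, and for the rest: "0 to 1 of the patients experienced GF, the study can be stopped for success".

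Section 3.2 says that follow-up will collect "use of defined treatments or procedures to support the graft function post-transplant". Section 3.4.5 spells these out and lists boost and DLI as items separate from HSCT. Section 7.1 has an efficacy endpoint on the use of transfusion for poor graft function, growth factors, boost or DLI, from HSCT to 3 years.

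**The concern.** The protocol treats boost and DLI as graft support, allows them while emapalumab is being given, and reads efficacy from a count of graft failures in 4, 7 or 10 patients. There is no control group to share the rescue rate. If a failing graft takes after a second cellular intervention, the GF count falls for a reason that may not be the drug. A lower count makes a futility stop less likely and a success stop more likely. At stake is whether a success reading at 7 patients can be presented as an effect of emapalumab when the next step is a pivotal study. Growth factors raise the same question for the ANC part of the engraftment definition.

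**Working it through.** **The plan's own figures.** Section 12.1 sizes accrual: 4/0.30 = 13.3, so 14 (stated 15), and 4/0.10 = 40 (stated 40). These reproduce to within one patient. No error rate or power is stated for the section 12.2 guidance, so there is nothing to reproduce there.

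**Step 1: how one patient is counted.** Take a patient given a boost or DLI after first dose and before GF is declared.
- The treatment is authorized (6.2) and not prohibited (6.3), so the patient stays evaluable (11.1.4, 12.4).
- Section 11.1.2 stops treatment for GF or a needed re-transplant; boost and DLI are not named there.
- If ANC and chimerism then meet section 3.4.4, engraftment is confirmed and no primary GF is recorded under section 7.
- Section 12.2 therefore adds nothing to the GF count.

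If GF is declared first, the patient is an event and the issue does not arise.

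**Step 2: effect of a single patient at 7.** Take one GF and one rescued graft among 7.
- As written: 1/7, which permits a success stop. Clopper-Pearson 95% CI 0.4% to 57.9%.
- With rescue counted: 1 + 1 = 2/7, which means continue. 95% CI 3.7% to 71.0%.

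The two intervals overlap almost entirely. The decision turns on the counting rule, not on the strength of the evidence.

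**Step 3: illustration with an ineffective drug.** Inputs:
- GF risk in CXCL9-positive patients without rescue: 0.86, the positive predictive value in section 1.1.2, from 26 HLH transplants.
- Share r of failing grafts rescued and scored as no GF: an assumption, as the documents give none.
- Effective risk: p = 0.86 × (1 − r), with patients independent.

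P(success at 7) = (1 − p)^7 + 7p(1 − p)^6. The look at 4 does not alter this, because 0 or 1 GF in 7 implies at most 1 in the first 4.

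P(futility at 4) = 4p³(1 − p) + p⁴.

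| r | p | P(success at 7) | P(futility at 4) |
|---|---|---|---|
| 0 | 0.860 | 0.000001 + 0.000045 = 0.005% | 0.356 + 0.547 = 90% |
| 25% | 0.645 | 0.0007 + 0.0090 = 1.0% | 0.381 + 0.173 = 55% |
| 50% | 0.430 | 0.0196 + 0.1032 = 12.3% | 0.1813 + 0.0342 = 22% |

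**Step 4: range.** At r = 10% and risk 0.86, success at 7 is still below 0.1%, and futility at 4 is 78%. At r = 75%, success is 53.6%. With assumed underlying risks instead of 0.86, success at 7 for r = 0, 25% and 50% is 0.4%, 4.8% and 23.4% at a risk of 0.70, and 6.3%, 19.4% and 44.5% at a risk of 0.50.

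**The case against.** The strongest case against has four parts.

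- **The counting is inferred.** No sentence says that a rescued graft counts as GF pre-empted. Primary GF has no operational definition in the supplied text, and section 12.5 defers full details to a SAP that is not part of it. This stands as a condition: a GF definition or rescue rule in that SAP could settle the matter.
- **Rescued patients are visible.** Section 7.1 reports boost and DLI use, section 12.5.2 plans estimates with 95% CIs for efficacy endpoints in the selected cohort, and the DDC and IDMC review data on very few patients. A reader might infer that drug and rescue cannot be told apart at all. The documents do not support that. What remains is narrower: the endpoint pools four kinds of support over 3 years, does not isolate use between first dose and engraftment, and does not feed section 12.2.
- **A definition could deal with it.** A reader might infer that no tightening of the engraftment definition would catch these patients. Section 3.4.4 shows otherwise: one arm of the secondary-GF definition already requires platelets to hold without transfusion.
- **The rule is soft and the size unknown.** Section 12.2 is guidance, the wording at 7 is permissive, and section 12.5 calls all analyses exploratory. This lowers the weight of the point but does not remove it, since the guidance can still end the study.

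**Conclusion.** The gap is real on the supplied text. A boost or DLI given after first dose and before GF is declared leaves the patient evaluable, and later engraftment keeps that patient out of the GF count that drives the looks at 4 and 7. One such patient is enough to move the reading at 7 from continue to success.

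The probabilities are illustrations only. They rest on an ineffective drug, on a predictive value from 26 HLH patients carried over to a wider population, and on rescue shares that are assumed. A reader might start from a lower risk, such as 43%, where rescue of half the failing grafts raises success at 7 from 12% to 54%. The documents give no source for that risk. If 43% were the risk on emapalumab (half of 86%), the figures would describe an active drug being called a success. At the only GF risk that the protocol states for CXCL9-positive patients, the success probability stays at or below about 1% until the rescue share exceeds a quarter. The futility look is more sensitive: it falls from 90% to 55% at that share.

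This is a worthwhile, inexpensive clarification of the analysis. It does not show that the trial would reach a wrong conclusion.

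**What to change.** Leave section 6.2 unchanged. In sections 7 and 12.2 and the SAP:

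1. Add a pre-specified sensitivity version of the main endpoint in which a boost or DLI between first dose and confirmed engraftment counts as failure of pre-emption.
2. List the recorded reason for each boost or DLI, so that use for reasons other than a failing graft can be separated. List growth-factor use alongside.
3. Show both counts to the IDMC and DDC at 4, 7 and 10 patients.
4. State the rule for disagreement: a success conclusion at 7 is described as a drug effect only if the sensitivity count is also 0 to 1. Otherwise the discordance is reported and the result is treated as not separable from rescue.

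If the SAP already contains such a rule, a cross-reference in section 12.2 is enough.

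The cost is SAP and protocol wording and one extra table row. Tables 6a and 6b already record concomitant medications during treatment; the sponsor should confirm that the date and reason of each boost or DLI are captured. The downside is that the sensitivity count may be less favourable, and that it will over-count failures where support was given for another reason, which is why the reasons are listed.
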